18.2. Reporting Adverse Events to ICR-CTSU

Any toxicity, sign or symptom that occurs after commencement of pembrolizumab treatment and within 90 days of the last administration of pembrolizumab, or 30 days following cessation of treatment if the patient initiates new anti-cancer therapy, whichever is earlier, and which is not unequivocally due to recurrence of disease, should be considered an AE.

All AEs must be reported on the relevant CRF and submitted to ICR-CTSU.

The severity of AEs should be graded according to the National Cancer Institute Common Terminology Criteria for Adverse Events (NCI CTCAE) v4.0. For each AE, the highest grade observed since the last visit should be reported.

Abnormal laboratory findings that meet the criteria for grade 2 or above toxicity as defined by NCI CTCAE v4.0 are considered to be clinically significant and should be reported as AEs. Whenever one or more toxicity/sign/symptom corresponds to a disease or a well-defined syndrome only the main disease/syndrome should be reported.

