11.4. Assessments at discontinuation of pembrolizumab treatment

On the **day of the last administration of pembrolizumab treatment** (or at the next planned visit if treatment discontinuation occurs between cycles), the following assessments should be conducted:

- Concomitant medication review
- Review of adverse events
- Full physical examination, ECOG performance status, vital signs
- Safety Blood tests: clotting (INR or PT/ aPTT), haematology (ANC, platelets, haemoglobin), biochemistry (hepatic function (bilirubin, ALT, AST, ALP and GGT), renal function (serum creatinine or estimated GFR (using Cockcroft-Gault)), thyroid function (T3, T4 TSH), glucose (random)
- Urinalysis
- Research blood samples for ctDNA analysis (at treatment discontinuation only):
 - o 2 x 10ml collected in ctDNA preservation tubes

Approximately **30 days after the last administration of pembrolizumab treatment or before initiation of a new anti-cancer treatment, whichever comes first,** the following assessments should be conducted:

- Review of adverse events
- Safety Blood tests: clotting (INR or PT/ aPTT), haematology (ANC, platelets, haemoglobin), biochemistry (hepatic function (bilirubin, ALT, AST, ALP and GGT), renal function (serum creatinine or estimated GFR (using Cockcroft-Gault)), thyroid function (T3, T4 TSH), glucose (random)

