- 3. Follow up bloods for patients who complete pembrolizumab or discontinue prematurely should be taken every 3 months in line with the start of ctDNA surveillance. For example if a patient goes on to receive treatment due to a positive ctDNA result at the 12 month ctDNA surveillance blood sample and then completes the full 12 months of pembrolizumab treatment, bloods will be taken at month 27, 30, 33, 36 and 39 from the start of ctDNA surveillance, and if a patient discontinues at month 7 bloods would be taken at month 21, 24, 27, 30 and 33 from start of surveillance
- 4. Written informed consent must be obtained from the patient prior to pre-treatment assessments being conducted.
- 5. Full physical examination includes height (prior to first dose of pembrolizumab only), weight (required prior to first dose of pembrolizumab and cycles 4, 8, 12 and 16 only), ECOG performance status and vital signs (heart rate, blood pressure).
- 6. Consent for imaging is included in registration PIS and ICF following implementation of protocol v6.0 onwards. Patients should undergo imaging immediately upon confirmation of a ctDNA positive result. The same investigations conducted as part of staging for the original primary breast cancer should be repeated. Patients who did not have imaging at diagnosis should have imaging in line with local guidelines for high risk disease.
- 7. Patients should be followed-up in line with standard practice every 6 months (+/- 1 month) from start of ctDNA surveillance. During post treatment follow up this can be conducted as a telephone call to the patient. Patients should be asked about relapse of breast cancer or other change in medical history. A recurrence tumour tissue sample should be provided at relapse for each patient who has tissue available from a biopsy taken routinely as part of standard patient care.
- 8. Pregnancy test should be done within 72hrs of first administration of pembrolizumab treatment.
- 9. With the exception of the end of treatment assessments, safety blood tests should be conducted within 72 hours prior to each cycle of pembrolizumab.
- 10. During pembrolizumab treatment, 2 x 10ml of blood should be collected in ctDNA preservation tubes on day 1 (pre-dose) of each cycle and until completion or withdrawal of pembrolizumab treatment. For 1 year after the administration of the last dose of pembrolizumab, 2 x 10ml of blood should be then collected every 3 months (+/- 2 weeks).

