17.15. Discontinuation and subsequent therapy

In cases where toxicity does not resolve to grade 0-1 within 12 weeks after the last infusion, pembrolizumab should be discontinued. Patients with a laboratory adverse event still at grade 2 after 12 weeks post last infusion may restart pembrolizumab if asymptomatic and only after consultation with the Chief Investigator.

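### Adverse events are reportable to 90 days after the last dose, but the last scheduled review is at about day 30; separately, the SAE cut-off after new therapy conflicts between sections

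*Protocol*

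**What the plan says.** **Reporting period.** Protocol 18.2 defines as an adverse event "Any toxicity, sign or symptom that occurs after commencement of pembrolizumab treatment and within 90 days of the last administration of pembrolizumab". The window shortens to 30 days after cessation if new anti-cancer therapy starts, whichever is earlier. It then adds: "All AEs must be reported on the relevant CRF and submitted to ICR-CTSU". Nothing limits this to serious events.

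**Scheduled reviews.** Section 11.4 asks for a review at discontinuation (on the day of the last dose, "or at the next planned visit if treatment discontinuation occurs between cycles"). It asks for a final one about "30 days after the last administration of pembrolizumab treatment or before initiation of a new anti-cancer treatment, whichever comes first". In the 11.7 table the adverse event row ends at the safety visit, which is headed 30 days post discontinuation. Section 11.5 then lists only 3-monthly ctDNA bloods and 6-monthly recurrence follow-up.

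**Later contact.** At the 6-monthly contact, 11.7 footnote 7 says: "Patients should be asked about relapse of breast cancer or other change in medical history".

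**SAEs.** Sections 3.3.1 and 11.7 footnote 2 give 90 days for SAEs, ending when new anti-cancer treatment is initiated. Section 18.3 gives 90 days after the last dose, or 30 days after cessation if new therapy starts, whichever is earlier.

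**Late events.** Section 17.12 warns that immune-type events, serious or not, can appear months after the last dose. Section 17.6 tells centres to watch for signs of immune-mediated reactions and sets no end date.

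**The concern.** The protocol sets a 90-day window for all adverse events and then schedules no review in most of it. A site working from the 11.7 table last asks about adverse events at about day 30. The 90-day notes beside that schedule, in 3.3.1 and footnote 2, speak of SAEs only. Section 17.11.1 also ends concomitant-medication recording 30 days after the last dose, so treatment given for a later event need not be recorded there.

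What is at stake is the record that 18.2 itself demands, above all non-serious immune events with onset in days 31 to 90. Without a scheduled question, capture depends on whether the patient volunteers the event and whether the site acts on 17.6.

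The SAE cut-off is a second problem of a different kind. Here two sections give different end dates for the same patient once new therapy starts.

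**Working it through.** **1. Days of the window with no scheduled review**

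Inputs: window of 90 days (18.2); final review at about day 30 after the last dose (11.4) or 30 days after discontinuation (11.7 table); cycle length 21 days (11.7 footnote 1); toxicity hold of up to 12 weeks = 84 days, from 17.15: "In cases where toxicity does not resolve to grade 0-1 within 12 weeks after the last infusion, pembrolizumab should be discontinued".

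Formula: gap = 90 − day of the last scheduled review, not below 0.

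| Type of stop | Last review, day after last dose | Gap, days |
|---|---|---|
| At a dose | 30 | 90 − 30 = 60 |
| Between cycles, 11.4 wording | 30 | 90 − 30 = 60 |
| Between cycles, 11.7 heading | 21 + 30 = 51 | 90 − 51 = 39 |
| After a 12-week hold, discontinuation review | 84 | 90 − 84 = 6 |
| After a 12-week hold, 11.7 heading | 84 + 30 = 114 | 0 |

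These are days, not shares of events.

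If new therapy starts on day t, the window ends at day 30, taking cessation as the last dose. For t of 30 or more there is no gap. For t below 30 the review comes before day t, so about 30 − t days follow it.

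**2. Does the footnote 7 contact fill the gap?**

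Footnote 3 gives two examples for a patient positive at month 12. For a full course, "bloods will be taken at month 27, 30, 33, 36 and 39 from the start of ctDNA surveillance". For an early stop, "if a patient discontinues at month 7 bloods would be taken at month 21, 24, 27, 30 and 33 from start of surveillance".

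Assumptions: treatment starts 28 to 42 days after the month-12 sample; a month is 30.44 days; month 7 means month 7 of treatment. Days are counted from the month-12 sample.

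- *Full course, 17 cycles.* Last dose at 28–42 + 16 × 21 = 364–378. Month 24 (day 365) is day −13 to +1 from the last dose. Month 27 (457) is day 79–93. Month 30 (548) is day 170–184.
- *Stop at month 7.* Stop at 28–42 + 213 = 241–255. Month 21 (274) is day 19–33. Month 24 (365) is day 110–124.

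The 6-monthly contacts are months 24 and 30. Nominally none falls in days 31–90 in either example. The ±1 month window could bring the second patient's month-24 contact to about day 80. The 3-monthly blood visits come closer (day 79–93 in the full-course case), but carry no adverse event review.

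**3. SAE cut-off**

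Let new therapy start on day t after the last dose, t up to 90. Sections 3.3.1 and footnote 2 end SAE reporting at day t. Section 18.3 ends it at day 30, again taking cessation as the last dose. The difference is |t − 30| days. For t below 30, 3.3.1 is shorter, by up to 30 days. For t above 30, 3.3.1 is longer, by up to 90 − 30 = 60 days.

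**The case against.** The strongest reply is that 18.2 sets a reporting period and 11.4 and 11.7 set visits. A period that outlasts the last solicited review can be deliberate: ask up to day 30, then report what comes to light. That stands as far as it goes. A reader might infer that 18.2 contradicts the schedule on non-serious events, but it does not. A site can comply with every section, and neither 3.3.1 nor footnote 2 says that non-serious reporting stops at day 30.

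A reader might also infer that sites have no prompt at all after day 30. Section 17.6 is a prompt, 17.12 warns of late onset, and 18.2 asks for the highest grade since the last visit while patients still attend for blood. None of these is a scheduled review, so the gap remains, but it is not silence. The eCRF guidance (22.2) and central checks (22.3) may also help; their content is not shown.

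Finally, a reader might infer that the safety secondary endpoint is biased. Section 19.3.2 ties that summary to the treatment period, so the documents do not support this.

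The objection leaves one thing unanswered: following the schedule yields a weaker record than 18.2 requires. It does not touch the SAE conflict in 3.3.1 and 18.3, so it would also be wrong to say that SAE reporting is wholly unaffected.

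**Conclusion.** The concern holds, at minor severity. For patients who stop at a dose without recurrence or new therapy, up to 60 of the 90 days have no scheduled adverse event review, and late non-serious immune events may be under-recorded. Sixty days is the upper bound. The 39-, 6- and 0-day cases depend on when discontinuation is recorded and on which section's 30 days are used.

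The affected patients are a subset of the 24 to 45 planned for pembrolizumab in the 19.1.2 table, and the protocol gives no figure for its size. The visit timings rest on the assumed 4 to 6 week start delay. How many events would be missed cannot be estimated from the document. No stated analysis is harmed: the primary endpoints and the treatment-period safety summary stand.

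The SAE cut-off after new therapy is a genuine inconsistency and needs one rule.

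**What to change.** In 11.5 and the 11.7 schedule, add an adverse event review at each existing 3-monthly ctDNA visit after the day-30 review, up to the first visit on or after day 90 from the last dose. Record events with onset up to the 18.2 cut-off. Align 3.3.1 and 11.7 footnote 2 with 18.2 and 18.3, including the 30-day rule after new therapy.

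The text cost is one schedule entry, one footnote and one sentence in 3.3.1. Patients already attend for blood and the adverse event form exists, so the burden is a few minutes at one or two visits. Recall is about 3 months: 91 days nominally, or 91 + 14 + 14 = 119 at the extremes of the ±2 week windows. No safety bloods are added, so symptom-free laboratory events after day 30 would still surface only through unscheduled tests.

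Cutting non-serious reporting to 30 days would also remove the mismatch. It is not recommended, because it gives up the late immune events that 17.12 warns about.

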18.3. Reporting of Serious Adverse Events to ICR-CTSU

Any SAE that occurs after the commencement of pembrolizumab treatment and up to 90 days following the last dose of pembrolizumab, or 30 days following cessation of treatment if the patient initiates new anticancer therapy, whichever is earlier, must be reported.

Any SAEs that occur more than 90 days after the last dose of pembrolizumab that, in the opinion of the Principal Investigator (or designated investigator), are related to pembrolizumab should be reported to ICR-CTSU if the Principal Investigator (or designated investigator) becomes aware of them.

All SAEs should be reported to ICR-CTSU within 24 hours of the Principal Investigator (or designated investigator) becoming aware of the event, by completing the c-TRAK TN SAE form and email to:

The ICR-CTSU safety team

Email: [contact]

Copying in the c-TRAK TN trial team

Email: [contact]

As much information as possible, including the Investigator's assessment of causality, must be reported to ICR-CTSU in the first instance. Additional follow up information should be reported as soon as it is available.

All SAE forms must be completed, signed and dated by the Principal Investigator or designated investigator.

All reported SAEs and follow up information will be forwarded to Merck, Sharp & Dohme upon receipt at ICR-CTSU.

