In KEYNOTE-012, the main toxicities of any grade included arthralgia (18.8%), fatigue (18.8%), myalgia (18.8%) and nausea (15.6%). There were five grade 3 treatment related adverse events: anaemia, aseptic meningitis (successfully treated with pembrolizumab interruption and steroids for 6 weeks, with reintroduction of pembrolizumab at a reduced dose), lymphopenia, headache and pyrexia. The patient who had aseptic meningitis had a prolonged partial response and remained on treatment for more than 17 months. There was one treatment related death due to disseminated intravascular coagulation in a patient who had with rapidly progressive disease having had three previous lines of treatment. There were a total of three immune related toxicities; grade 3 colitis (reported 40 days after the last pembrolizumab dose and after starting capecitabine), grade 3 hepatitis and grade 2 hypothyroidism[26]. Pembrolizumab may be given safely in combination with radiotherapy with no apparent increase in adverse effects [27-29]. Pembrolizumab has been given concurrently with adjuvant radiotherapy in completed and ongoing phase III trials (NCT03725059, NCT03036488).

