3.3. Follow-up

3.3.1. Patients who receive pembrolizumab treatment

A safety assessment should be conducted for each patient approximately 30 days after the last administration of pembrolizumab treatment or before initiation of a new anti-cancer treatment, whichever comes first (see section 11.4). SAEs that occur within 90 days of the end of treatment, and before initiation of a new anti-cancer treatment, should also be reported, followed and recorded. Any SAEs that occur more than 90 days after the last dose of pembrolizumab that, in the opinion of the Principal Investigator (or designated investigator), are related to pembrolizumab should be reported to ICR-CTSU if the Principal Investigator (or designated investigator) becomes aware of them.

Patients should be followed up every 6 months (+/- 1 month) from start of ctDNA surveillance until disease recurrence (see section 13), unless the patient specifically withdraws consent for follow up (see section 12) or until centres are advised that no further follow up is required.

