11.7. Schedule of assessments for pembrolizumab treatment group

	Pre-treatment	Pembrolizumab Treatment Cycles			Cvcles	End of Treatment		Post-Treatment		
	Screening					C4-	Discontinuation	Safety Follow-up	-	Up Visits
	Day -28 to Day-1	С	1	C2	C3	C17	(max 12 months)	, ,		
									Every 3 months	Every 6 months
									from the start of	from start of
									ctDNA	ctDNA surveillance
									surveillance for	until disease
				- 1					12 months	recurrence
Duranda and Anna and an		D1		D1 ¹	D1 ¹ -	D41	At the set	30 days post	following	(+/- 1 month)
Procedures & Assessments:		-72	D1	-			At time of Discontinuation	discontinuation ²	treatment discontinuation ³	
		hrs	D1	-	72hrs				discontinuation	
Written informed consent ⁴	v	1	1	Admi	nistrati	ve Proce	edures			
Inclusion/exclusion criteria	X X									
	X									
Demographics and medical history										
Concomitant medication review	X	Х		Х	Х	Х	Х			
Eligibility confirmation to ICR-CTSU	Х									
Full shorted an estimation 5	v.	V		1	1	-	essments			
Full physical examination ⁵	X	Х		Х	Х	Х	Х			
Imaging ⁶	Х			v	v	v	V	V		
Review adverse events Pembrolizumab administration ¹			х	X X	X X	X X	Х	Х		
Disease recurrence ⁷			^	^	^	^				Х
Disease recurrence	Laborato	ny Proc	oduros	//	monts: a	nalvsis	performed by LOCAI	laboratory		^
Pregnancy test – urine or serum β -	X	ITY FICE	euures	A336331	nents. a	111019515				
HCG^8	~									
Clotting ⁹	Х	Х		Х	Х	Х	Х	Х		
Haematology ⁹	Х	Х		Х	Х	Х	Х	Х		
Biochemistry ⁹	Х	Х		Х	Х	Х	Х	Х		
Thyroid function ⁹	Х	Х		Х	Х	Х	Х	Х		
Hepatic function ⁹	Х	Х		Х	Х	Х	Х	Х		
Renal function ⁹	Х	Х		Х	Х	Х	Х	Х		
Glucose ⁹	Х	Х		Х	Х	Х	Х			
ECG	Х									
Urinalysis	Х	Х		Х	Х	Х	Х			
				r	arch Blo	r				
Blood sample for ctDNA analysis ¹⁰		Х		Х	Х	Х	Х		Х	
Blood sample for PBMC isolation ¹¹		Х			Х					

ICR-CTSU

- 1. Day 1 of each treatment cycle is the day of pembrolizumab treatment administration. All assessments, including sample collection, should be performed within 72 hours prior to day 1. Each cycle should be 21 days in length. Day 1 of each cycle should be planned for 21 days (+/- 72 hours) from day 1 of the previous cycle.
- 2. SAEs that occur within 90 days of the end of treatment and before initiation of a new anti-cancer treatment, whichever comes first, should be reported, followed and recorded.

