18.1.2. Serious Adverse Event (SAE)

An SAE is any untoward medical occurrence that occurs after the commencement of trial treatment and within 90 days of the last administration or 30 days following cessation of treatment if the patient initiates new anti-cancer therapy, whichever is earlier, and:

- results in death,
- is life-threatening
- requires hospitalisation or prolongation of existing inpatients' hospitalisation
- results in persistent or significant disability or incapacity
- is a congenital anomaly or birth defect

Important adverse events that are not immediately life-threatening or do not result in death or hospitalisation but may jeopardise the patient or may require intervention to prevent one of the other outcomes listed in the definition above, may also be considered serious.

In addition, adverse events meeting either of the criteria listed below, are reportable to the ICR-CTSU in the same timeframe as SAEs to meet certain local requirements. Therefore, these events are considered serious by ICR-CTSU for collection purposes.

- Is a new cancer (that is not a condition of the study)
- Is associated with an overdose

Recurrence of the indicated disease and death due to recurrence of the indicated disease are not considered SAEs.

Pregnancy whilst participating in a trial is not itself considered an SAE but should be followed up for congenital anomalies or birth defects.

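### When new anti-cancer therapy starts within 90 days of the last pembrolizumab dose, the SAE reporting rules contradict each other and leave related events before day 91 under no rule

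*Protocol*

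**What the plan says.** **Section 18.** The SAE definition in 18.1.2 contains a time window: "within 90 days of the last administration or 30 days following cessation of treatment if the patient initiates new anti-cancer therapy, whichever is earlier". Section 18.2 uses the same limits for AEs: "or 30 days following cessation of treatment if the patient initiates new anti-cancer therapy, whichever is earlier, and which is not unequivocally due to recurrence". Section 18.3 repeats them for SAE reporting: "or 30 days following cessation of treatment if the patient initiates new anticancer therapy, whichever is earlier, must be reported".

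**Sections 3.3.1 and 11.7.** These have no 30-day term. Section 3.3.1 says "SAEs that occur within 90 days of the end of treatment, and before initiation of a new anti-cancer treatment, should also be reported". Footnote 2 of the schedule in 11.7 says "SAEs that occur within 90 days of the end of treatment and before initiation of a new anti-cancer treatment, whichever comes first, should be reported".

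**Late events.** Sections 3.3.1 and 18.3 carry the same sentence. It begins "Any SAEs that occur more than 90 days after the last dose of pembrolizumab that, in the opinion of the Principal Investigator" and asks for a report if the investigator judges the event related and becomes aware of it.

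**The concern.** The late-event sentence appears designed to take over where the main window stops. It does so only when the window runs to day 90. When new anti-cancer therapy closes the window earlier, the late rule still waits for day 91. A reaction attributed to pembrolizumab can then be outside the rules on day 45 and inside them on day 91, and no reason is given.

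The protocol expects late reactions: sections 1.2.3 and 17.12 both say they may occur several months after the last dose. It also expects the situation that shortens the window. Section 3.3.1 is read by patients' teams alongside 3.2.1, under which patients who recur must stop pembrolizumab and should receive standard treatment for recurrence, and section 1.2.1 describes recurrence in ctDNA-positive patients as close to inevitable.

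At stake are the site's 24-hour report, the Chief Investigator's causality and expectedness review (18.4), expedited SUSAR reporting (18.5) and the IDMC's safety review (19.5).

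**Working it through.** No design figure is involved. The check lays the rules out by day after the last dose and asks, for a related SAE on each day, whether any rule makes it reportable.

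**Conventions.** Day 0 is the last dose, and cessation is taken as the same day. New therapy starts on day t, with t no later than 90. Under 3.3.1 and 11.7 an event must come before initiation, so day t itself is outside.

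**Rules.**
- 18.3, literal: covered to day 30 if new therapy is started, otherwise to day 90. Related SAEs are covered again from day 91. Gap: days 31-90, which is 90 - 30 = 60 days, whatever t is.
- 18.3, narrower reading: the 30-day term applies only if new therapy starts by day 30. Gap: 60 days if t is 30 or less, otherwise none.
- 3.3.1 and 11.7 footnote 2: covered to day t - 1. Related SAEs are covered again from day 91 (the 3.3.1 sentence). Gap: days t to 90, which is 91 - t days.

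**Results: days on which a related SAE is not reportable.**

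| New therapy starts | 18.3 literal | 18.3 narrower | 3.3.1 / 11.7 | Days on which literal 18.3 and 3.3.1 disagree |
|---|---|---|---|---|
| never | none | none | none | none |
| day 10 | 31-90 (60) | 31-90 (60) | 10-90 (81) | 10-30 (21) |
| day 45 | 31-90 (60) | none | 45-90 (46) | 31-44 (14) |
| day 60 | 31-90 (60) | none | 60-90 (31) | 31-59 (29) |
| day 80 | 31-90 (60) | none | 80-90 (11) | 31-79 (49) |

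The direction of the disagreement changes. For a day-10 start, 3.3.1 is the narrower rule: an SAE on day 20 is reportable under 18.3 but not under 3.3.1. For a day-60 start on the literal wording, section 18 is the narrower: an SAE on day 45 is reportable under 3.3.1 but not under 18.3. On the narrower reading of 18.3, a day-60 start produces disagreement on days 60-90 instead (31 days).

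**The definition.** Because 18.1.2 puts the window inside the meaning of SAE, an event after the window is not an SAE. Section 18.1.3 defines a SAR as a kind of SAE, and 18.1.4 defines a SUSAR as a kind of serious adverse reaction, so the later event is none of these as defined. This also conflicts with the late-event sentence itself, which speaks of SAEs beyond 90 days.

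**Other routes.** The AE window in 18.2 closes at the same point as 18.3. The events of clinical interest in 18.1.5 carry no stated window but cover only overdose and one pattern of liver tests. After recurrence, sections 11.6 and 13 require no further follow-up. None of these fills the gap.

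**The case against.** Shortening collection once another anti-cancer drug is given is a legitimate choice, because attribution becomes harder. That defends a shorter window for all SAEs. It does not explain why an SAE the investigator does attribute to pembrolizumab should be left out before day 91 and reported after it.

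The narrower reading of the 30-day term in 18.3 is also reasonable, and under it patients who start new therapy after day 30 have no gap in that section. This stands, but the gap remains for those who start by day 30, and 3.3.1 and 11.7 are unaffected by it.

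Four stronger inferences are tempting, and the protocol does not support them:

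- *That reporting under 18.3 stops on the day new therapy starts.* That is the rule in 3.3.1 and 11.7. Under 18.3 the gap opens on day 31.
- *That the colitis case in section 1.2.3 would go unreported under every version.* The text describes "grade 3 colitis (reported 40 days after the last pembrolizumab dose and after starting capecitabine" in the cited phase Ib study. It gives neither the onset date nor the date capecitabine began, and does not say that the event was serious; grade 3 is not a seriousness criterion in 18.1.2. If capecitabine began on days 31-39, the narrower reading of 18.3 would cover an SAE on day 40. The case shows that the situation is realistic and no more.
- *That the safety endpoint is under-counted.* Section 19.3.2 assesses safety over the treatment period, and the gap lies after it.
- *That a large share of treated patients, or of their events, is lost.* The protocol gives no timing for new therapy after the last dose. Days without cover are not missed events.

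**Conclusion.** The point holds as an internal contradiction with a reporting gap. It applies only to patients who start new anti-cancer therapy within 90 days of the last dose; for everyone else the main window and the late rule meet at day 90/91.

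Per affected patient, the gap is 60 days under the literal 18.3 wording and 91 - t days under 3.3.1 and 11.7. These figures rest on taking cessation as the day of the last dose. How many patients are exposed could lie anywhere between none and all of those treated, since the protocol gives no basis for a figure.

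The consequence is that a related serious reaction could properly be withheld from SAR and SUSAR assessment and from the IDMC by a site following the text, and that two sites could treat the same event differently. No primary endpoint, sample size or success criterion changes.

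**What to change.** 1. In 3.3.1 and 18.3, replace the day-90 trigger of the late-event sentence with *after the end of the SAE reporting window, however it closed*, so that every SAE judged related stays reportable.
2. In 18.1.2, state that such later related events still count as SAEs, so that the SAR and SUSAR definitions follow.
3. Give 3.3.1, footnote 2 of 11.7, 18.1.2, 18.2 and 18.3 one closing rule for new anti-cancer therapy, and say whether any 30-day term depends on when that therapy starts.

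Step 3 should be a deliberate choice. Copying the literal section 18 wording into 3.3.1 and 11.7 would remove days 31-59 for a day-60 start. SAEs the investigator judges unrelated on those days would then not reach the Chief Investigator's review.

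The cost is a wording amendment in five places and a few more SAE forms, with no new visits or tests. The gain is limited to events the investigator becomes aware of, because follow-up ends at recurrence.
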